**Efficacy of regular, musical and electric toothbrushes in plaque removal in children –
A randomized clinical trial**

DATED: 04/08/2024

STUDY PROTOCOL

Study design

This study is designed as a randomized clinical trial to compare the efficacy of three types of toothbrushes - regular, musical, and electric - in removing supragingival plaque among children aged 6-12 years. The study duration was set for 2 months, beginning on January 15, 2024.

Ethical approval

Ethical approval (no. 07-06-43) was sought from the Local Committee of Bioethics at Jouf University, KSA. All necessary approvals were obtained prior to the initiation of the study to ensure ethical compliance and participant safety.

Sample size calculation

Sample size estimation was done by using GPower software (version 3.0). Sample size was estimated for F test and ANOVA: Repeated measures, between factors, for 3 groups and 4 follow up measurements was chosen. A minimum total sample size of 102 was found to be sufficient for an alpha of 0.05, power of 95%, 0.25 as effect size. As the proposed study is a trial of 60 days duration with 4 repeated measurements, so keeping in mind a 10% attrition, the sample size was inflated to 111 (37 per group).

Participant selection

A total of 111 healthy children participated in the study, each selected based on specific inclusion and exclusion criteria. Written consent was obtained from the parents or guardians of all participants.

Inclusion criteria

- Children aged 6-12 years;

- Cooperative children; and
- Children with a minimum of twenty teeth.

Exclusion criteria

- Children with poor oral hygiene characterized by extrinsic stains or calculus deposits;
- Presence of any oral lesions;
- Presence of malocclusion; and
- Medically compromised patients.

Randomization and allocation

Participants were randomly allocated to one of three groups (n = 37 participants per group) using a computer-generated randomization sequence managed by the first examiner. The groups are defined as follows:

- **Group 1 (Regular Toothbrush):** Oral-B Chhota Bheem Toothbrush.
- **Group 2 (Musical Toothbrush):** Aqua White Musical Chhota Bheem Toothbrush.
- **Group 3 (Electric Toothbrush):** Oral-B Star Wars Kids Electric Toothbrush.

Table 1 allocate steps for randomization of the process.

Blinding

To reduce bias, the second examiner, responsible for recording clinical parameters, was blinded to the group assignments.

Intervention

Participants and their guardians were instructed in the horizontal scrub technique and asked to adhere to a brushing regimen of two minutes, twice daily, for 45 days. Standard fluoride toothpaste and a diary for recording brushing experiences was also provided. Guardians supervised brushing to ensure compliance and prevent the use of other oral hygiene measures.

Outcome measures

The primary outcome measure is the Plaque Index (Quigley and Hein). Plaque assessments was conducted at baseline (day 0) and on days 15, 30, and 45. Participants were refrain from oral hygiene for 24 hours before each recall visit. During each visit, they were supposed to brush under supervision for two minutes with their assigned toothbrush and toothpaste. Plaque disclosure was achieved using a 5 mL disclosing solution for 15 seconds, followed by rinsing with 10 mL water for 10 seconds.

Data collection

All clinical data was recorded using a standardized proforma. The principal investigator ensured the accuracy and confidentiality of the data, entering it into a data sheet immediately after collection. Confidentiality was maintained by anonymizing survey responses and securely storing the data.

Data management plan

The data management plan includes continuous monitoring by the principal investigator, secure transfer and storage of data, and adherence to safety and ethical protocols.

Potential risks and benefits

The study presents minimal risks, mainly limited to potential discomfort from brushing or allergic reactions to toothpaste. However, the potential benefits include improved oral hygiene awareness and a reduction in plaque, contributing to better oral health outcomes for the participants.

This detailed methodology ensures a clear, structured approach to conducting the trial, adhering to CONSORT¹³ guidelines for reporting randomized clinical trials. The study, self-funded, aimed to contribute valuable insights into paediatric dental care practices and enhance oral health education for parents and guardians, aligning with the goals of the CONSORT guidelines for transparent reporting of clinical trials.

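### The test used to size the trial leaves the day-0 Plaque Index out as a covariate; if that test is the analysis, precision is lost, by an amount that depends on an unstated within-child correlation

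*Protocol*

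**What the plan says.** Under Sample size calculation the protocol states: "Sample size was estimated for F test and ANOVA: Repeated measures, between factors, for 3 groups and 4 follow up measurements was chosen". It continues: "A minimum total sample size of 102 was found to be sufficient for an alpha of 0.05, power of 95%, 0.25 as effect size". The total is then raised to 111, or 37 per group, for attrition. No within-child correlation is given.

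Under Outcome measures the Quigley and Hein Plaque Index is the primary outcome, with this schedule: "Plaque assessments was conducted at baseline (day 0) and on days 15, 30, and 45". That is one baseline and three post-baseline scores.

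The same section has children brush under supervision with the assigned brush at each visit. It does not say whether plaque is scored before or after that brushing. The 24-hour break from oral hygiene is tied to recall visits. The protocol has no section on statistical analysis.

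**The concern.** A child's plaque score before treatment usually predicts that child's later scores. The between-factors repeated-measures ANOVA compares group averages over the measurements and has no place for a covariate. If it is used as named, the part of the between-child variation that day 0 could explain stays in the error term, and intervals for the brush contrasts are wider than the data require.

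The count of four adds to this. Only three scores follow baseline, so four measurements agree with the schedule only if day 0 is one of the responses. The one role the text implies for day 0 is therefore as an outcome, at a time when no brush effect should yet exist.

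**Working it through.** **Inputs.** From Sample size calculation: N = 102, three groups, f = 0.25, alpha = 0.05, target power 95%. From Outcome measures: day 0 plus days 15, 30 and 45. Assumptions, not in the protocol: one correlation r between any two visits (compound symmetry), the same effect at all three follow-ups, f defined on the single-visit SD, and day 0 scored before the assigned brush is used.

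**Method.** Power is from the noncentral F with df1 = 2. The noncentrality is λ = f²N / v, where v is the variance of the analysed quantity relative to a single score, and f²N = 0.0625 × 102 = 6.375.

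**Step 1: the plan's own figure.** With four responses, v = (1 + 3r)/4 and df2 = 99.
- r = 0.2: v = 0.40, λ = 15.94, power 95.0%. The smallest balanced N reaching 95% is 102, so the stated figure reproduces, but only with this unstated r.
- r = 0.5: v = 0.625, λ = 10.20, power 81.1%. Reaching 95% would need 159.

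**Step 2: mean of days 15, 30 and 45, without and with day 0 as covariate.** Unadjusted: v = (1 + 2r)/3, df2 = 99. Adjusted: v = (1 + 2r)/3 − r², df2 = 98.

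| r | v unadj. | v adj. | λ unadj. | λ adj. | Power unadj. | Power adj. | Gain (points) |
|---|---|---|---|---|---|---|---|
| 0.1 | 0.400 | 0.390 | 15.94 | 16.35 | 95.0% | 95.5% | 0.5 |
| 0.2 | 0.467 | 0.427 | 13.66 | 14.94 | 91.3% | 93.6% | 2.3 |
| 0.3 | 0.533 | 0.443 | 11.95 | 14.38 | 87.2% | 92.7% | 5.5 |
| 0.4 | 0.600 | 0.440 | 10.63 | 14.49 | 82.8% | 92.9% | 10.1 |
| 0.5 | 0.667 | 0.417 | 9.56 | 15.30 | 78.4% | 94.2% | 15.8 |
| 0.6 | 0.733 | 0.373 | 8.69 | 17.08 | 74.2% | 96.3% | 22.1 |
| 0.7 | 0.800 | 0.310 | 7.97 | 20.56 | 70.2% | 98.5% | 28.3 |

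With all 111 children analysed, the gain is 1.9 points at r = 0.2 and 13.8 at r = 0.5. The residual variance ratio, adjusted to unadjusted, is 0.427/0.467 = 0.91 at r = 0.2 and 0.417/0.667 = 0.625 at r = 0.5.

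**Step 3: day 0 as one of four responses.** If day 0 carries no group effect, the averaged effect shrinks to 3/4, so λ from Step 1 is multiplied by 9/16.
- r = 0.2: λ = 15.94 × 0.5625 = 8.96, power 75.5%.
- r = 0.5: λ = 10.20 × 0.5625 = 5.74, power 55.0%.

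The adjusted analysis is 18 and 39 points better, but two changes are mixed here. At r = 0.2, dropping day 0 as a response takes power from 75.5 to 91.3%, and the covariate adds the step to 93.6%. At r = 0.5 the steps are 55.0 to 78.4 to 94.2%. Only the last step in each is the gain from adjustment.

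**Step 4: a weakly correlated baseline.** With zero correlation between day 0 and follow-up, and r = 0.5 among follow-ups, power is 78.38% without the covariate and 78.37% with it.

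**The case against.** The strongest objection is that the quoted sentence is a sample-size setting. A trial can be sized on a simple F test and analysed with a covariate. The primary model is commonly left to the SAP, which is not at hand, and nothing in the protocol excludes adjustment. This stands: a reader might infer that the protocol commits to an unadjusted analysis and has already given up power, but the text does not show that. The loss is conditional on the named test being the analysis.

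The second concerns size. A reader might take 16 points as this trial's loss. That figure needs r = 0.5, which the protocol neither states nor supports, and at which its own 102 gives 81.1% instead of 95%. At r = 0.2 the gain is about 2 points. In turn, r = 0.2 is only solved back from the sample size and is not a supported estimate, so a range is the honest statement.

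The third concerns the comparator. The protocol never names an unadjusted three-visit mean. Set against its own four-measurement calculation, which assumes the full effect at all four, the adjusted analysis changes power by −1.4 points at r = 0.2 (95.0 to 93.6%) and +13.1 at r = 0.5 (81.1 to 94.2%). That is correct, but an equal effect at day 0 is not a plausible premise if day 0 is a true baseline.

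The fourth is that adjustment might be thought free of cost or bias. It is safe only if day 0 precedes use of the assigned brush, and the protocol does not give the order. A score taken after brushing is post-treatment, and adjusting for it could remove part of the effect. Day 0 may also be scored under different conditions, since the hygiene break is tied to recall visits; that would weaken the correlation.

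Lastly, a reader might infer that randomisation is unstratified. The protocol refers to a Table 1 for its steps, and that table is not in the text at hand, so no inference about strata is made here.

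**Conclusion.** The point holds as a conditional one. The only between-group test named has no baseline covariate, and it fits the schedule only with day 0 as a response. If it is the analysis, precision is lost. At N = 102 and f = 0.25, the gain from using day 0 as covariate for the follow-up mean is about 2 points at r = 0.2, 5 to 6 at r = 0.3 and 16 at r = 0.5. These figures rest on compound symmetry, an equal effect at the three follow-ups, a day-0 score taken before the assigned brush is used, and an r that the protocol does not state. Adjustment also makes the design less dependent on that unknown: for r from 0.2 to 0.7, adjusted power stays between about 93 and 98%, while unadjusted power falls from 91 to 70%. The documents do not support a fixed loss of 16 points, or the claim that an unadjusted analysis has been prespecified.

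**What to change.** State the primary comparison as ANCOVA of the mean Plaque Index over days 15, 30 and 45 on group, with day-0 Plaque Index as covariate. A mixed model on those three visits with group, visit, group-by-visit and day-0 Plaque Index would serve equally. Day 0 should not also be a response. Report the three pairwise brush contrasts from that model.

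State the order of scoring and supervised brushing at day 0, since the adjustment is sound only if the score comes first. Give the correlation assumed in the sample size and mark it as an assumption.

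The cost is a few sentences and one degree of freedom, with no added children, visits or data. If day 0 correlates weakly with follow-up, the gain shrinks towards zero and almost no power is lost.

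### Raising 102 to 111 does not cover the stated 10% attrition: about 100 children would remain, 2 below the protocol's own minimum

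*Protocol*

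**What the plan says.** The Protocol, under *Sample size calculation*, names the method: "Sample size was estimated for F test and ANOVA: Repeated measures, between factors, for 3 groups and 4 follow up measurements was chosen". It gives the result as "A minimum total sample size of 102 was found to be sufficient for an alpha of 0.05, power of 95%, 0.25 as effect size". It then moves from that minimum to the number enrolled: "keeping in mind a 10% attrition, the sample size was inflated to 111 (37 per group"). Attrition is the only reason given for the increase, and no inflation formula is shown.

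The total recurs under *Participant selection* ("A total of 111 healthy children participated in the study") and the group size under *Randomization and allocation* ("Participants were randomly allocated to one of three groups (n = 37 participants per group")). So 111 is the intended and randomised number, not a misprint.

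**The concern.** An attrition allowance is meant to ensure that, if the expected fraction of participants is lost, the number left still meets the calculated minimum. A reader of the sample size paragraph will assume that 111 does this for 102 at 10% loss. The increase from 102 to 111 is 9/102 = 8.8%, already below 10%. An increase of d per cent also protects against a loss of less than d per cent, because the loss applies to the larger, enrolled number. The stated allowance therefore looks undelivered. What is at stake is the accuracy of a sample size statement that is likely to be carried into the trial report, and possibly a small amount of power.

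**Working it through.** **Inputs (Protocol, *Sample size calculation*).** Minimum total 102, which is 34 in each of 3 groups; attrition 10%; enrolled total 111, 37 per group; alpha 0.05; power 95%; effect size 0.25, read as Cohen's f; 4 measurements; between-factors test of a repeated-measures ANOVA.

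**How 111 can be obtained.** Marking up each group by 10% gives 34 × 1.10 = 37.4. Rounded down this is 37, and 3 × 37 = 111. This matches the printed form of the figure, but it is an inference, since the protocol gives no formula.

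**What 10% cover requires.**
- Division: N/(1 − d) = 102/0.90 = 113.3. Per group, 34/0.90 = 37.8, so 38 per group and 114 in total. Check: 114 × 0.90 = 102.6, which is at least 102.
- Mark-up on the total: N(1 + d) = 102 × 1.10 = 112.2.

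Both exceed 111.

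**What 111 delivers.**
- At 10% loss: 111 × 0.90 = 99.9. In whole children, 11 losses (11/111 = 9.9%) leave 100. Per group, 37 × 0.90 = 33.3 against 34.
- Tolerance: 111 − 102 = 9 losses, and 9/111 = 8.1%.

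**Cost in power.** For the between-groups F test with k = 3 groups and m = 4 measurements, the noncentrality is λ = f²·N·m / (1 + (m − 1)r), with 2 and N − 3 degrees of freedom. The correlation r between repeated measures is not stated, so every value below is an assumption.

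For example, at r = 0.20 and N = 102, λ = 0.0625 × 102 × 4 / 1.6 = 15.94; at N = 100, λ = 15.63.

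| Assumed r | Power, N = 102 | Power, N = 100 | Loss (points) |
|---|---|---|---|
| 0.185 | 95.6% | 95.2% | 0.4 |
| 0.20 | 95.0% | 94.6% | 0.4 |
| 0.3 | 90.8% | 90.2% | 0.6 |
| 0.5 | 81.1% | 80.3% | 0.85 |

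Over r from 0 to 0.95 the largest loss is 0.95 points. Values of r from about 0.185 to 0.20 reproduce 102 as the smallest equal-group total for 95% power. The protocol does not say that such a value was used. The rows for r = 0.3 and 0.5 serve only to show that the loss stays small. Their low absolute power comes from the assumed correlation, not from the attrition allowance; at those values 95% power would need 123 and 159 children.

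**The case against.** The best defence is that this is a rounding matter with no practical effect. A 10% mark-up per group gives 37.4, and dropping 0.4 of a child yields exactly the printed 37 per group. The total is 3 short of 114, or 3/111 = 2.7%, and the sentence mentions attrition loosely without promising 102 completers. At the lower end of the correlations that reproduce 102 (r about 0.185), 100 completers would still have 95.2% power, so missing 102 need not mean missing the power target. The protocol also reports enrolment in the past tense, and its date falls after the planned two months from January 15, 2024. If the trial ran to schedule, actual losses now matter more than planned ones.

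Much of this stands, and it is why the point is minor. It does not remove the error. Rounding down explains 111 but does not restore the cover, and a minimum has to be rounded up to remain a minimum. The sentence gives a specific percentage and a specific total as its consequence, so a reader will test one against the other. The result at r = 0.185 depends on a correlation the protocol does not give, whereas the shortfall against 102 follows from the protocol's own figures.

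**Conclusion.** The concern holds, as a minor arithmetic error. The total of 111 covers 8.1% attrition, not 10%; at 10% about 100 children remain against a stated minimum of 102. This conclusion needs only the three numbers in the sample size paragraph. The statement that the power loss is below 1 point rests on the between-factors F test, an effect size f of 0.25 and an assumed correlation anywhere from 0 to 0.95.

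The finding does not show the trial to be materially underpowered, and the number enrolled is not disputed. Nor does it settle whether 102 gives 95% power: that depends on the correlation between repeated measures, which the protocol does not state.

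**What to change.** No further enrolment is needed. Replace the attrition sentence under *Sample size calculation* with wording such as: *The total of 111 (37 per group) keeps the minimum of 102 for up to 9 losses (8.1%); at 10% attrition about 100 completers are expected.* If the power at 100 completers is to be reported, compute it from the correlation actually used in the sample size calculation, not from an assumed value. The cost is one corrected sentence, with no change to enrolment, design or analysis.
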